1.2. Current therapy for removal of an adnexal mass

Surgical exploration for an adnexal mass may be performed laparoscopically (conventional or robotic) or by laparotomy. The choice of surgical approach depends upon the degree of suspicion of malignancy and surgeon and patient preference. Ovarian cancer staging can be performed using an open or laparoscopic approach, although the majority of surgeons in current practice prefer laparotomy if there is a high degree of suspicion of malignancy. If there is a low or moderate suspicion of malignancy, a laparoscopic approach is typically used. Laparoscopy is associated with a shorter recovery and decreased perioperative morbidity compared with laparotomy.

The surgical technique used must minimise the potential for tumour disruption or dissemination. If malignancy is suspected, oophorectomy is required rather than ovarian cystectomy. Women with early stage ovarian cancer (i.e. no malignant cells in ascites or peritoneal cytology) benefit from removal of the adnexal mass intact, since opening the mass results in a more advanced stage and adversely affects prognosis (11, 12). In addition, every attempt must be made to provide the pathologist with an ovarian specimen with an intact cortex. If a laparoscopic approach is used, the ovary can be placed in a tissue recovery bag. If the specimen is too large to remove through the existing incisions, cyst fluid may be aspirated (but the collapsed cyst should not be disrupted) or the incision may be enlarged. The practice of morcellating ovarian masses in a bag is discouraged

because it may compromise pathology evaluation. In general, aspiration of cyst contents is not advisable as the sole surgical intervention because no tissue is obtained for histopathology and cytology of cyst fluid is not reliable for exclusion of malignancy, and there is a high rate of recurrence. Recent years have witnessed the use of a posterior colpotomy to retrieve large benign ovarian lesions since removal through the umbilicus may not be straightforward (13).

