using a reusable bipolar grasping forceps before being cut using cold scissors. The ovarian ligament is coagulated and cut. The infundibulopelvic ligament is coagulated and cut. The adnexa is resected. If necessary, the same procedure is repeated for the contralateral side. The peritoneal cavity is rinsed and haemostasis is checked.

Small and benign adnexa will be removed directly through the wound protector part of the NOTES port. Large adnexa or adnexa that are macroscopically suspicious, will be placed in an endobag (Memobag, Teleflex). The purse string of the endobag is pulled through the wound protector and the purse string is released. The content of the cyst is aspirated to reduce the volume of the adnexa. The endobag is now removed with the adnexa inside it. The vNOTES port is removed.

The colpotomy is closed using three interrupted figure-of-eight Vicryl 2/0 sutures. A vaginal plug (betadine gauze 10cmx5m) is placed to be removed after 3 hours together with the Foley catheter.

Antibiotic administration:

Cefazolin 2g and metronidazol 1.5g are administered IV during the procedure.

Analgesia at the recovery room and the nursing ward: The pain management for both groups was discussed with two senior staff members of the department of anaesthesiology of the hospital, who are co-investigators. The protocol will be standard for both comparison groups and is presented in appendix V.

The vaginal plug and the Foley catheter are removed 3 hours after the surgery. The bandages are left in place and not changed unless soaked by blood with a need to change. The personnel of the recovery room will be asked to replace bandages only for hygienic reasons and immediately to apply a new wound dressing without revealing any information to the participant or personnel on the outpatient or hospitalization ward.

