4.1.2 LSC adnexectomy

This is the surgical procedure done in the control arm of the NOTABLE trial.

Clindamycin vaginal cream is administered on admission of the study participant to the outpatient ward.

The woman is placed in lithotomy position in a vacuum mattress. The abdomen, the vulva and the vagina are disinfected with an alcoholic betadine solution and draped. A Foley catheter is inserted into the bladder.

A small vertical intra-umbilical skin incision is made. A Verress needle is inserted into the peritoneal cavity; the correct position of the needle tip is checked with Semm test. CO₂ is insufflated until a maximal intraperitoneal pressure of 15mmHg. The Verress needle is removed and replaced by a 10mm reusable trocar. An optic is inserted through the 10mm trocar and the peritoneal cavity is inspected. The patient is now placed in Trendelenburg position. Two reusable 5mm trocars are placed under direct vision in the left and right iliac fossa lateral of the epigastric vessels. The small intestine is lifted out of the pelvis.

The ureter is identified, but not routinely dissected. It is only dissected if it cannot be identified transperitoneally. The proximal end of the Fallopian tube is coagulated at its origin into the uterus using a reusable bipolar grasper and cut using cold scissors. The ovarian ligament is coagulated and cut. The infundibulopelvic ligament is coagulated and cut. The adnexa are resected and placed in an endobag (Memobag, Teleflex). If necessary, the same procedure is repeated for the contralateral side.

The peritoneal cavity is rinsed and haemostasis is checked. No drains are left in the peritoneal cavity except when there might be any uncertainty concerning the haemostasis. The 5 mm trocars are removed under direct vision. The purse string of the endobag is pulled through the 10 mm trocar upon removal of the optic. The umbilical incision is extended vertically in caudal direction, the size being not more than 2.5 cm. The fascia and peritoneum are opened and the proximal end of the endobag is pulled through the incision without causing any rupture if possible. If not possible, the endobag should be opened and the content of the cyst should be aspirated to reduce the volume of the adnexa. The aspirated fluid should be send for cytological examination. The endobag is now removed with the adnexa inside it.

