4.1.3 Failure of procedure

Occasionally, surgical removal of a benign adnexal mass by any of the two techniques may not be completed according to the random sequence generation because of technical limitations or unexpected findings such as extensive adhesions or unexpected malignancy. Successful vNOTES or laparoscopic removal of a benign adnexal mass is possible in the majority of women, but the probability of success is not readily predictable. In cases where the intended procedure has to be abandoned, the appropriate technique (e.g. staging laparotomy for ovarian cancer) or a second procedure (e.g. laparoscopy or laparotomy after bowel preparation) under general anaesthesia should be scheduled as soon as possible. Women who require an alternative more appropriate intervention or a second procedure are not excluded or withdrawn from the NOTABLE trial. The investigators will sensitively explain to them that follow-up information is still very important,

despite the change in treatment, and unless they wish to withdraw completely from the trial, they will be followed up.

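### Section 4.1.1 aspirates bagged vNOTES adnexa without the intact-delivery-first condition of 4.1.2, so read literally a bagged mass that could come out whole is aspirated needlessly (minor wording correction)

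*Protocol*

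**What the plan says.** Protocol section 4.1.1 (vNOTES) sorts specimens before extraction. "Small and benign adnexa will be removed directly through the wound protector part of the NOTES port". The rest are bagged: "Large adnexa or adnexa that are macroscopically suspicious, will be placed in an endobag (Memobag, Teleflex"). The two triggers for bagging are alternatives, so a suspicious adnexa is bagged whatever its size. The purse string is then drawn through the wound protector and released, and the next sentence reads "The content of the cyst is aspirated to reduce the volume of the adnexa". The bag is removed after that. The section mentions neither an attempt to deliver the mass intact nor any examination of the fluid.

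Section 4.1.2 (laparoscopy) bags every adnexa. The umbilical incision is extended to at most 2.5 cm, and then "the proximal end of the endobag is pulled through the incision without causing any rupture if possible". Aspiration is the fallback: "If not possible, the endobag should be opened and the content of the cyst should be aspirated to reduce the volume of the adnexa". It adds: "The aspirated fluid should be send for cytological examination".

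Section 1.2 gives the clinical reason for caution. Women with early ovarian cancer "benefit from removal of the adnexal mass intact, since opening the mass results in a more advanced stage and adversely affects prognosis". The same section accepts aspiration when the specimen is too large for the incisions, provided the collapsed cyst is not disrupted, and it names enlarging the incision as the alternative.

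**The concern.** The two arms use the same product (the same brand of endobag) and openings of comparable size, yet the written extraction rules differ. The control arm protects a mass that can come out whole. The experimental arm, as worded, does not.

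The gap falls mainly on the adnexa bagged because it looks suspicious rather than because it is big. That is the mass for which section 1.2 most wants intact removal. At stake are the safety of the occasional woman with such a mass and the consistency of specimen handling between the arms.

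**Working it through.** The protocol gives no figure for how often bagged masses are aspirated or delivered whole, so there is nothing to reproduce. The check is a comparison of the texts.

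| Step | vNOTES (4.1.1) | Laparoscopy (4.1.2) |
|---|---|---|
| Which adnexa are bagged | Large, or macroscopically suspicious | All |
| Opening | 2.5 cm colpotomy | Umbilical incision, at most 2.5 cm |
| Intact delivery tried first | Not stated | Yes, where possible |
| Aspiration | Stated without condition | Only if intact delivery fails |
| Purpose given for aspiration | Volume reduction | Volume reduction |
| Cytology of the aspirate | Not stated | Required |

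1. **Does the sorting step in 4.1.1 supply the missing condition?** Partly. It takes small benign adnexa out of the bagging route, which explains why 4.1.1 needs the condition less often than 4.1.2. It does not cover a bagged mass that could pass whole. There are two such groups: the small suspicious adnexa, and any mass called large that would still fit. Section 4.1.1 gives no diameter at which an adnexa becomes large.

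2. **Does the purpose clause supply it?** It points that way, but 4.1.2 gives the same purpose in nearly the same words and still writes the condition out separately. In this protocol the clause states why aspiration is done, not when.

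3. **Does the route explain the difference?** The document gives no reason for trying intact delivery through one opening and not the other. The stated sizes are the same at their maximum.

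4. **Does another section supply it?** Section 4.1.3 deals with procedures that cannot be completed as allocated because of "unexpected findings such as extensive adhesions or unexpected malignancy". It does not govern how a bagged mass is delivered. No other section sets a delivery or cytology rule for vNOTES.

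5. **How many women?** This cannot be derived. Section 3.2 requires a mass presumed benign on the IOTA simple rules and excludes solid masses and high suspicion of malignancy, so the number is probably very small. As context only, the cohort of presumed-benign masses described in section 1.4.1 had 5% borderline and 3.7% invasive lesions, together 5% + 3.7% = 8.7%. This shows that preoperative selection does not remove every non-benign mass; it is not an estimate for this trial.

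**The case against.** The best defence is that the sentence limits itself. Aspiration is done to shrink the specimen, and a mass that already fits needs no shrinking. Sections 1.2 and 5.2 also treat aspiration as something done out of need, and the trial's aim is removal without spill. One surgeon, the principal investigator, performs every operation, so divergent readings between operators cannot arise. What remains is a narrow subset: cystic, suspicious at surgery despite a benign scan, and deliverable whole in a bag. Even there, aspiration takes place inside a bag already drawn through the wound protector. Cytology is marginal, because section 1.2 itself calls cyst-fluid cytology unreliable for excluding malignancy, the whole adnexa goes to pathology in any case, and no trial outcome uses the result.

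Most of this stands and sets the size of the point. It does not remove it: the condition is written in one arm and absent from the other, and a surgical instruction should not depend on the reader inferring it.

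Two stronger readings are tempting, and the documents support neither.

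- A reader might infer that the wording builds extra failures into the vNOTES arm and so biases the primary outcome or costs power. Section 5.2 counts as failure a need to aspirate in order to remove the mass. It does not say how an aspiration done without need would be scored, and the protocol gives no frequency for one. Any power figure would rest on two assumptions with no basis in the text.
- A reader might infer from the 8.7% that roughly that share of women is exposed. Those masses measured 8 to 13 cm and were triaged by other criteria. Many would be bagged and need volume reduction under either rule.

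**Conclusion.** The point holds as a minor safety and arm-consistency correction. Section 4.1.1 states aspiration of bagged adnexa unconditionally, where 4.1.2 makes it a fallback. Followed to the letter, it aspirates a mass that could have left the body whole, contrary to the principle in 1.2. The purpose clause makes it likely that this was not meant.

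The conclusion rests on reading the two procedure sections as instructions to be followed as written, and on no other section filling the gap. It does not assume that the surgeon would in fact aspirate a deliverable cyst. The number affected is probably very small and cannot be calculated, the harm is limited by containment in the bag, and no effect on the primary outcome is claimed. The missing cytology step is the lesser part.

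**What to change.** Amend the extraction paragraph of section 4.1.1 to match 4.1.2: deliver bagged adnexa intact through the colpotomy where this can be done without rupture, and aspirate inside the bag only where intact delivery is not possible. As a secondary alignment, send any vNOTES aspirate for cytology, as the laparoscopic arm already does.

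The cost is a wording amendment and a cytology test on any vNOTES aspirate. No patients, visits or analyses are added, and the sample size does not change.

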4.1.2 LSC adnexectomy

This is the surgical procedure done in the control arm of the NOTABLE trial.

Clindamycin vaginal cream is administered on admission of the study participant to the outpatient ward.

The woman is placed in lithotomy position in a vacuum mattress. The abdomen, the vulva and the vagina are disinfected with an alcoholic betadine solution and draped. A Foley catheter is inserted into the bladder.

A small vertical intra-umbilical skin incision is made. A Verress needle is inserted into the peritoneal cavity; the correct position of the needle tip is checked with Semm test. CO₂ is insufflated until a maximal intraperitoneal pressure of 15mmHg. The Verress needle is removed and replaced by a 10mm reusable trocar. An optic is inserted through the 10mm trocar and the peritoneal cavity is inspected. The patient is now placed in Trendelenburg position. Two reusable 5mm trocars are placed under direct vision in the left and right iliac fossa lateral of the epigastric vessels. The small intestine is lifted out of the pelvis.

The ureter is identified, but not routinely dissected. It is only dissected if it cannot be identified transperitoneally. The proximal end of the Fallopian tube is coagulated at its origin into the uterus using a reusable bipolar grasper and cut using cold scissors. The ovarian ligament is coagulated and cut. The infundibulopelvic ligament is coagulated and cut. The adnexa are resected and placed in an endobag (Memobag, Teleflex). If necessary, the same procedure is repeated for the contralateral side.

The peritoneal cavity is rinsed and haemostasis is checked. No drains are left in the peritoneal cavity except when there might be any uncertainty concerning the haemostasis. The 5 mm trocars are removed under direct vision. The purse string of the endobag is pulled through the 10 mm trocar upon removal of the optic. The umbilical incision is extended vertically in caudal direction, the size being not more than 2.5 cm. The fascia and peritoneum are opened and the proximal end of the endobag is pulled through the incision without causing any rupture if possible. If not possible, the endobag should be opened and the content of the cyst should be aspirated to reduce the volume of the adnexa. The aspirated fluid should be send for cytological examination. The endobag is now removed with the adnexa inside it.

The fascia is closed using a Vicryl-1 running suture. The umbilicus and the other incisions are disinfected with Betadine solution. The skin incisions are closed with a monocryl 3/0 intradermal

suture and steri-strips. The wound sites are covered with a standard bandage. A vaginal plug (betadine gauze 10 cm x 5 m) is placed to be removed after 3 hours together with the Foley catheter.

Antibiotic administration:

Cefazolin 2g and metronidazol 1.5g are administered IV during the procedure.

Analgesia at the recovery room and the nursing ward: The pain management for both groups was discussed with two senior staff member of the department of anaesthesiology of the hospital, who are co-investigators. The protocol will be standard for both comparison groups and is presented in appendix V.

The vaginal plug and the Foley catheter are removed 3 hours after the surgery. The bandages are left in place and not changed unless soaked by blood with a need to change. The personnel of the recovery room will be asked to replace bandages only for hygienic reasons and immediately to apply a new wound dressing without revealing any information to the participant or personnel on the day care unit or hospitalisation ward.

The decision to discharge or to admit to hospital for the night will be based solely on the choice of the woman to return home the same day or stay overnight. The outcome assessor will report this decision in the patient record without consulting the results of the pain scoring or whether or not additional analgesics were administered. Every woman leaving the hospital will be given a standard list with instructions not to have intercourse during six weeks and not to work for a period of four weeks. Telephone numbers will be provided for contacting the staff members on call in case urgent medical care for treating any adverse event is needed. Cefazolin 2g is administered IV before discharge.

4.1.3 Failure of procedure

Occasionally, surgical removal of a benign adnexal mass by any of the two techniques may not be completed according to the random sequence generation because of technical limitations or unexpected findings such as extensive adhesions or unexpected malignancy. Successful vNOTES or laparoscopic removal of a benign adnexal mass is possible in the majority of women, but the probability of success is not readily predictable. In cases where the intended procedure has to be abandoned, the appropriate technique (e.g. staging laparotomy for ovarian cancer) or a second procedure (e.g. laparoscopy or laparotomy after bowel preparation) under general anaesthesia should be scheduled as soon as possible. Women who require an alternative more appropriate intervention or a second procedure are not excluded or withdrawn from the NOTABLE trial. The investigators will sensitively explain to them that follow-up information is still very important,

despite the change in treatment, and unless they wish to withdraw completely from the trial, they will be followed up.

4.2. Concomitant interventions and treatments

It is anticipated that most women presenting with a suspected benign adnexal mass will require no further intervention other than removal of the adnexa. However, in some circumstances additional treatments may be considered necessary by the responsible clinician at the time of adnexal removal or subsequently. Surgical interventions in the form of endometrial ablation or hysterectomy may subsequently be necessary and the need for such interventions will be recorded. However, if the need for additional surgery *at the time* of surgery is indicated, then such patients are excluded for recruitment to the NOTABLE trial. All therapeutic interventions additional to removal of one or both adnexa will be recorded and as the trial is randomised we anticipate that these further interventions will be symmetrically applicable.

4.3. Withdrawal from the NOTABLE trial

All women who consent to the randomised NOTABLE trial, should be followed up and asked to complete postal questionnaires, regardless of actual treatment received.

If a woman specifically requests a treatment setting *after* randomisation, then her choices should be respected. This does not necessitate withdrawal from the trial. Similarly, if one of both procedures fails, she will require subsequent treatment. In both circumstances, it should be sensitively explained to them that follow-up information is still very important, and unless they wish to withdraw completely from the trial, they will be followed up. Any request to withdraw from follow-up should be notified to the NOTABLE study nurse.

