3.3. Randomisation

If the woman is eligible for the NOTABLE trial, the trial secretary will obtain a randomised allocation the day before surgery. This will be done using a randomisation list generated by a free computer software program offered by Research Randomizer (<https://www.randomizer.org>). The random sequence generation will be concealed using sequentially numbered opaque sealed envelopes. The envelope will be opened by the nurse assistant on the day of surgery for practical logistic reasons. We will use stratified randomisation according to the cyst diameter. See 3.5 Stratification of randomisation.

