3.4. Patients with strong preference for treatment

A minority of women will express a clear preference for one of both treatments (e.g. strong desire to have no scar) and for this reason will not wish to be randomised between surgical treatments. To investigate how outcomes vary by choice, these women could be followed up in exactly the same way as for those women randomised into the NOTABLE trial. We will however not do any formal non-randomised follow-up of these women for simple logistical reasons.

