4. TREATMENT ALLOCATIONS

4.1. Surgical procedures

The principal investigator, who has training and experience in both laparoscopy and NOTES, will perform all surgical procedures. He is therefore not blinded. All vNOTES participants will be blinded by three superficial “mock” skin incisions similar to those routinely done with the laparoscopic technique. The wound bandages will be left in place until the day 7 postoperative control to be removed by the coordinating investigator who will state at that moment that the wound healing has left an almost invisible scar as expected. This procedure aims to blind the participants, personnel and outcome assessors. The practice of performing “mock” incisions should not be considered as unethical: it is a procedure that has already been used in some surgical trials to minimise performance and detection bias whenever a subjective outcome is measured (22). The decision to use “mock” surgery is based on the clinical equipoise regarding the balance between benefits and adverse events for the two interventions under comparison (23).

4.1.1 vNOTES adnexectomy

This is the surgical procedure done in the intervention arm of the NOTABLE trial.

Clindamycin vaginal cream is administered on admission of the study participant to the outpatient ward.

The patient is placed in lithotomy position in a vacuum mattress. The abdomen, the vulva and the vagina are disinfected with an alcoholic betadine solution and draped. A Foley catheter is inserted into the bladder.

Three superficial skin incisions are made, one deep in the umbilicus and one in the left and right iliac fossa lateral of the epigastric vessels, and in the suprapubic region. The small vertical intraumbilical skin incision is closed with a monocryl 3/0 intradermal suture. Wound bandages are applied to all three skin incisions.

A 2.5 cm posterior colpotomy is made using a cold knife. The pouch of Douglas is opened using cold scissors. A Gelpoint Mini (Applied Medical) is used as vNOTES port and is inserted into the pouch of Douglas. CO₂ is insufflated until a maximal intraperitoneal pressure of 15mmHg. An optic is inserted and the peritoneal cavity is inspected. The patient is now placed in Trendelenburg position. The small intestine is lifted out of the pelvis.

The ureter is identified, but not routinely dissected. It is only dissected if it cannot be identified transperitoneally. The proximal end of the Fallopian tube is coagulated at its origin into the uterus

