6.3. Statistical Analysis

We will calculate a 95% confidence interval of the difference in the proportions of women with a successful removal of an adnexal cyst. Non inferiority of the intervention (vNOTES) will be concluded

when 15% lies above the upper limit of this confidence interval. For this primary analysis, adjustments for prognostic factors will not be made in the first instance; the effect of the variables listed in Section 3.5 (Stratification of randomisation) will be explored as a secondary analysis. Continuous measures (VAS scores) will be analysed using analysis of covariance (adjusting for baseline value). Multilevel models for repeated measurements will also be used to compare the mean differences in VAS pain scores between groups overall at all time points, thereby maximising the power of the data available.

Analysis will be performed on an 'intention to treat' basis in the first instance as recommended in the CONSORT statement. A 'per protocol' analysis will also be performed to test the robustness of the results obtained. As a conservative measure, estimates of effect sizes between the two arms will be presented as point estimates with two-sided 95% confidence intervals. The trial can only conclude non-inferiority if 15% lies out of the upper band of the confidence interval (i.e. vNOTES 15% less successful than laparoscopic treatment).

Baseline characteristics of the patients enrolled in the two groups will be compared to ensure that randomisation has produced comparable groups of participants, and will be covariates in the modelling procedure.

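### Section 4.3 does not rule out a change of operation on request after randomisation; if such requests were granted, the intention-to-treat non-inferiority comparison would be diluted

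*Protocol*

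**What the plan says.** Four parts of the protocol bear on this point.

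- **4.3 (withdrawal).** "If a woman specifically requests a treatment setting" after randomisation, "then her choices should be respected. This does not necessitate withdrawal from the trial". All women who consent "should be followed up and asked to complete postal questionnaires, regardless of actual treatment received".
- **3.3 (randomisation).** On timing, "the trial secretary will obtain a randomised allocation the day before surgery". The sequence is concealed in numbered opaque sealed envelopes, and "The envelope will be opened by the nurse assistant on the day of surgery for practical logistic reasons". No hour is given, and nothing says whether this is before or after induction.
- **3.4 (strong preference).** A minority of women with a clear preference "for this reason will not wish to be randomised between surgical treatments". The example given is a strong wish to have no scar.
- **6.3 (analysis).** "Analysis will be performed on an 'intention to treat' basis in the first instance as recommended in the CONSORT statement". A per-protocol analysis is added to test robustness. Non-inferiority is concluded when the upper limit of the two-sided 95% interval for the difference is below 15%. The text does not ask that both analysis sets meet this.

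Section 4.1 adds mock skin incisions in the vNOTES arm: "This procedure aims to blind the participants, personnel and outcome assessors".

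**The concern.** A preference voiced before randomisation keeps a woman out of the comparison (3.4). The same preference voiced after it may leave her in the comparison, with her request granted (4.3). If the request concerns technique, a laparoscopy done by choice in the vNOTES arm is counted as a vNOTES result, and the reverse holds in the laparoscopy arm. Either way the arms become more alike. In a superiority trial this dilution is conservative. In a non-inferiority trial it works towards the claim whenever the new procedure is truly worse, which is the case the test must guard against.

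There is a second cost. A woman who receives the operation she asked for knows which one she had. Her decision on same-day discharge and her pain scores, both self-determined secondary outcomes under 5.3, are then no longer blinded.

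The point concerns a change by choice before the first incision. Procedure failure and conversion during surgery (4.1.3) are a different matter and belong in the allocated arm.

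**Working it through.** **The plan's own figure.** Inputs from 6.1: success 95% in both arms, margin 15 points, power 80%, one-sided test.

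n per arm = (1.645 + 0.842)² × 2 × 0.95 × 0.05 / 0.15² = 26.1, rounded up to 27, so 54 in total. Allowing for 15% drop-out, 54 / 0.85 = 63.5, rounded up to 64. Both stated figures are reproduced, at one-sided 5%. They are not in dispute here.

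**Effect of switching.** Inputs:

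- 33 women per arm (half of the final target of 66 in 6.1).
- True success by operation actually performed: 95% laparoscopy, 80% vNOTES, a deficit equal to the margin.
- Share s of an arm that has the other operation on request. The protocol gives no rate; 0%, 10% and 20% are assumed.
- A woman who switches has the success probability of the operation she receives.

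Success by allocated arm under intention to treat:

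- vNOTES to laparoscopy: p_V = 0.80 + 0.15s
- laparoscopy to vNOTES: p_L = 0.95 − 0.15s

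The probability of a claim is the sum of Bin(x; 33, p_L) × Bin(y; 33, p_V) over all pairs (x, y) for which the upper 95% limit of laparoscopy minus vNOTES is below 0.15. The Newcombe upper limit is d + √[(u_L − x/33)² + (y/33 − l_V)²], where d = x/33 − y/33, u_L is the upper Wilson limit for laparoscopy and l_V the lower Wilson limit for vNOTES. Wald limits are shown for comparison, because 6.3 does not name the interval method.

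| Switching | p_L | p_V | Difference | False claim, Newcombe | False claim, Wald |
|---|---|---|---|---|---|
| None | 0.950 | 0.800 | 15.0 points | 2.2% | 4.2% |
| 10% vNOTES to laparoscopy | 0.950 | 0.815 | 13.5 | 3.3% | 6.3% |
| 20% vNOTES to laparoscopy | 0.950 | 0.830 | 12.0 | 4.9% | 9.1% |
| 10% laparoscopy to vNOTES | 0.935 | 0.800 | 13.5 | 3.5% | 5.5% |
| 20% laparoscopy to vNOTES | 0.920 | 0.800 | 12.0 | 5.1% | 7.3% |
| 10% in both directions | 0.935 | 0.815 | 12.0 | 5.0% | 8.0% |

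Both directions dilute by a similar amount. This matters because the one preference that 3.4 names, the wish for no scar, points towards vNOTES.

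**Price of requiring both analysis sets.** Take both operations at 95% and exactly 3 of the 33 vNOTES women switching, so that the per-protocol comparison is 33 against 30. The same enumeration, with the switchers as a third binomial (n = 3), gives the chance of a correct claim. It falls from 59.2% (intention to treat alone) to 52.5% (both sets) with Newcombe limits, and from 80.7% to 75.0% with Wald limits. If nobody switches the two sets coincide for this purpose and nothing is lost.

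**The case against.** The strongest reply is that the protocol never grants a choice of operation. Section 4.3 speaks of a treatment setting, and the choice the protocol plainly gives women elsewhere is same-day discharge or an overnight stay. The envelope is sealed and opened by a nurse assistant, nothing says the woman is told, and 4.1 sets out to keep her blinded. She cannot react to an arm she does not know, a request made blind may match her allocation, and women with strong preferences are expected to decline under 3.4. A per-protocol analysis is planned.

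Much of this stands. A reader might infer that women may choose their operation once allocated, that the allocation is known while they are awake, or that the two sentences in 3.3 contradict each other. The documents support none of these. *Setting* is not *technique*. No hour is given for opening the envelope. An allocation obtained one day and opened the next is coherent.

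It does not close the gap. Discharge or overnight stay is already each woman's free choice in both arms, so a rule accommodating that as a request after randomisation would be largely redundant. The clause sits beside follow-up whatever treatment was received and beside failure of a procedure, so technique is not excluded. A woman need not know her arm to ask for one operation, and a granted request would undo the blinding.

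On size, the reply is also partly right. Without any switching, moving from Newcombe to Wald limits raises the error from 2.2% to 4.2%, more than 10% switching from vNOTES to laparoscopy does. The sample size itself was reproduced at one-sided 5%. But the decision rule uses a two-sided 95% interval, a nominal 2.5% on the relevant side, and that is the level being eroded.

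**Conclusion.** The point holds as an ambiguity with a conditional consequence. Section 4.3 leaves room for a change of operation by choice after randomisation, 3.3 does not prevent it, and 6.3 would score it in the allocated arm with per protocol only as a check on robustness. If such changes occurred and vNOTES were truly worse, the comparison would move towards non-inferiority.

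With a true deficit at the margin, 33 per arm and Newcombe limits, the false-claim rate goes from 2.2% to 3.3% at 10% switching from vNOTES to laparoscopy and to 4.9% at 20%. This rests on assumed switching rates and on switchers having the success rate of the operation they receive. A reader might conclude that the primary result is biased in favour of vNOTES. That goes too far: the documents neither grant the switch outright nor suggest that it would be frequent. The change is worth making because it is cheap and removes the question.

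**What to change.** 1. **3.3, 3.4, 4.1 and 4.3.** In 3.3, drop the allocation on the day before and have the numbered envelope for the woman's stratum taken and opened in theatre after induction of anaesthesia. A woman who voices a preference before then is not randomised, in line with 3.4. Her choice is still respected, but it can no longer fall after randomisation. State in 4.3 whether *setting* includes surgical technique, and reconcile it with 3.4 and with the blinding in 4.1. Sections 4.1.1 and 4.1.2 describe the same preparation in both arms up to the first incision, so this looks feasible. The cost is that both instrument sets must be ready for each case, and the logistic reasons that 3.3 gives for its present timing have to be weighed against it.

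2. **6.3.** Conclude non-inferiority only if the upper limit is below 15% in both the intention-to-treat and the per-protocol set. Define the per-protocol set so that it removes only women who received the other operation by choice before the first incision. Women with procedure failure or conversion stay in it. This costs no power if nobody switches, which the first change is meant to secure. If 3 of 33 did switch, it would cost about 6 to 7 percentage points.
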